Study title: Smartphone-based Self-care Education Program for Women With Interstitial Cystitis: Educational Remote IC Aide

PI: [name], MPH

Institution: University of Pennsylvania

NCT Number: 05260112

Document date: 02/02/2021

Protocol Details

Basic Info

Confirmation Number:	didaffdb
Protocol Number:	844895
Created By:	[name]
Principal Investigator:	[name]
Protocol Title:	Smartphone-based self-management program for women newly diagnosed with interstitial cystitis/bladder syndrome
Short Title:	ERICA
Protocol Description:	American Urological Association's 1st and 2nd line therapies such as patient education, bladder retraining, pelvic floor physical therapy, and mind-body therapies are highly effective management strategies for IC/BPS. We developed a smartphone-based program to remotely teach patients with IC/BPS how to self-manage their symptoms, and also provide support and guidance via clinically-validated messages. We plan to test the clinical efficacy of this program for 50 patients.
Application Type:	EXEMPT Category 3

Resubmission*

Yes

Hospital Sites

Will any research activities and/or services be conducted at a Penn Medicine affiliated hospital site?

No

Study Personnel

Principal Investigator

Name:	[name]
Dept / School / Div:	4333 - OB-Obstetrics and Gynecology
Campus Address	4283
Mail Code	
Address:	[name]
City State Zip:	[name]
[contact]
Fax:	-
Pager:	
Email:	[contact]
HS Training Completed:	Yes
Training Expiration Date:	
Name of course completed :	CITI Protection of Human Subjects Research Training - ORA
GCP Training Completed:	Yes
Training Expiration Date:	03/11/2023
Name of course completed :	Good Clinical Practice: An Introduction to ICH (GCP) Guidelines

Study Contacts

Name:	[name]
Dept / School / Div:	4628 - WM-Ctr for Res on Reprod and Women's Health
Campus Address	
Mail Code	
Address:	
City State Zip:	
Phone:	
Fax:	
Pager:	
Email:	[contact]
HS Training Completed:	Yes
Training Expiration Date:	
Name of course completed :	CITI Protection of Human Subjects Research Training - ORA
GCP Training Completed:	Yes
Training Expiration Date:	01/13/2023
Name of course completed :	Good Clinical Practice: An Introduction to ICH (GCP) Guidelines

Name:	[name]
Dept / School / Div:	4628 - WM-Ctr for Res on Reprod and Women's Health
Campus Address	
Mail Code	
Address:	[name]
City State Zip:	[name]
Phone:	
Fax:	
Pager:	
Email:	[contact]

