To recruit 50 patients, we anticipate 4-6 weeks to recruit and enroll patients on a rolling basis until we have all 50. Each subject will participate in the study for 6 weeks. We will begin recruiting as soon as we have IRB approval for this modification. For 50 patients to complete the program, we anticipate approximately 3-4 months. We plan to allot 1-2 months afterwards for data analysis and manuscript preparation.

Characteristics of the Study Population

Target population

Women newly diagnosed with interstitial cystitis/bladder pain syndrome. Inclusion criteria: women who have access to a smart phone with text messaging capability and are able to read and write English. Exclusion criteria: women with recurrent urinary tract infections, neurological conditions such as multiple sclerosis, recent (within 6 months) of surgery or pregnancy, prior radiation to pelvic area.

Subjects enrolled by Penn Researchers

50

Subjects enrolled by Collaborating Researchers

0

Vulnerable Populations

Children Form

Pregnant women (if the study procedures may affect the condition of the pregnant woman or fetus) Form

Fetuses and/or Neonates Form

Prisoners Form

Other

None of the above populations are included in the research study

The following documents are currently attached to this item:

There are no documents attached for this item.

Participant recruitment

Please describe the plan to equitably identify and recruit a diverse group of participants that is reflective of the population under study. If this is a multicenter protocol, the recruitment plan should describe the local (Penn) site's plan. Describe: how potential participants may be identified (review of medical records, Slicer Dicer, DAC reports including referrals from physician offices and clinics); who may approach potential participants; methods to achieve sample diversity and inclusiveness; what information may be presented to or discussed with them; and the context and setting in which recruitment will happen.

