Modification: [name], a urologist who specializes in IC/BPS and practices at Virtua Health, will disseminate information about the study to her patients who may be eligible. She will only inform them that there is a remotely-delivered self management education study conducted via Penn that they may be interested in and our study coordinator's contact information. She will not be responsible for recruitment, consent, or enrollment. Please note that no Virtua Health resources, including their electronic medical records, will be used. Prospective recruitment: Female patients with interstitial cystitis/bladder pain syndrome (IC/BPS) will be recruited from the clinical practices of Penn Urogynecology and Penn Urology. Urogynecology and urology providers outside of Penn can direct interested and eligible patients to the study. The study team will reach out to these patients to overview the program. Patients who are interested in participating will follow the same consent and enrollment process. We will also have a visual ad and accompanying text to be posted on social media accounts (Facebook, Instagram, Twitter) of IC Association (non-profit organization supporting patients with IC/BPS) [IRB and Penn social media committee APPROVED previously], and via video presentation

during ICA's self-care-oriented online event [Script APPROVED by the IRB]. Interested patients will have a phone call with one of the clinicians on the study team to confirm eligibility and undergo the same consent and enrollment process as those recruited from our clinical practices. Retrospective recruitment: Female patients with IC/BPS who were seen by a faculty practices of Urogynecology and Urology will be identified by retrospective chart review. These patients will be messaged using my PennMedicine patient portal to reply to the message if they are interested a potential research study (recruitment script attached). Overall, recruitment will end when 50 subjects have been recruited. At a time mutually agreed upon by the interested patient and a research team member, study information will be presented to them over the phone. Risks and benefits of participation in the study will be discussed. Consent form will be signed via Penn's RedCAP platform. <https://redcap.med.upenn.edu/surveys/?s=DE4R83PAJ3> Confidentiality will be maintained throughout the recruitment process as well as during study participation.

Recruitment Materials

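### Does the missing time window for a new diagnosis mean that the wrong women could be enrolled?

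*Protocol*

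**What the plan says.** The Protocol Title under Basic Info reads "Smartphone-based self-management program for women newly diagnosed with interstitial cystitis/bladder syndrome". The Target population section begins with "Women newly diagnosed with interstitial cystitis/bladder pain syndrome" and continues with "Inclusion criteria: women who have access to a smart phone with text messaging capability and are able to read and write English". The disease requirement therefore sits in the opening sentence, and so does the word *newly*. The exclusions in that paragraph include "recent (within 6 months) of surgery or pregnancy", the only recency term there with a stated window. The advertisement text under Use of Penn Media & Social Media Services also asks for a recent diagnosis, again without a window.

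Under Participant recruitment, the clinic route reads "Female patients with interstitial cystitis/bladder pain syndrome (IC/BPS) will be recruited from the clinical practices of Penn Urogynecology and Penn Urology", and the chart-review route reads "Female patients with IC/BPS who were seen by a faculty practices of Urogynecology and Urology will be identified by retrospective chart review". Neither gives a diagnosis date or a look-back period. For providers elsewhere the text is "Urogynecology and urology providers outside of Penn can direct interested and eligible patients to the study". For responders to social media or the online event it adds "Interested patients will have a phone call with one of the clinicians on the study team to confirm eligibility".

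The Overall objectives section speaks of testing the program in 50 patients with IC/BPS and says nothing about recency. The Procedures section limits consent to eligible participants and makes no exception by route.

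**The concern.** A restriction that appears in the title, the target population and the advertisement ought to be one that staff can apply. Without a window, two coordinators could classify the same woman differently and both be following the Protocol. The contrast with the 6-month window in the same paragraph makes the omission more noticeable. A search of women already seen in the practices is also the route most likely to turn up long-standing disease, and the text moves from identifying these women to messaging them with no date filter mentioned.

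The stake is interpretation. With one group and a before-after comparison, the mean change describes whoever was enrolled. If women with long-standing disease were included and the result were reported as applying to new diagnoses, the claim would not fit the cohort.

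**Working it through.** The Protocol gives no figure on this point to reproduce, so the check sets the passages side by side and then asks what the analysis depends on.

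**1. Where recency is stated.**

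| Place in the Protocol | Population named | Time window |
|---|---|---|
| Basic Info, Protocol Title | newly diagnosed | none |
| Target population, opening sentence | newly diagnosed | none |
| Target population, exclusions | surgery or pregnancy | 6 months |
| Overall objectives | patients with IC/BPS | not applicable |
| Participant recruitment, Penn clinics | women with IC/BPS | none |
| Participant recruitment, chart review | women with IC/BPS already seen | none |
| Social media advertisement | recently diagnosed | none |

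The factual part of the concern is correct: no section defines the term.

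**2. Does the recruitment text loosen eligibility?** It answers a form prompt on how potential participants may be identified. Compare what it says for the Penn clinic and chart-review routes with the Target population paragraph. Besides *newly*, that paragraph lists two inclusion criteria (smartphone access, English) and four exclusions (recurrent urinary infection, neurological conditions, recent surgery or pregnancy, pelvic radiation), so 2 + 4 = 6 items. The two routes repeat 0 of the 6. If silence there meant that a criterion was waived, all six would be waived on those routes, which nobody would read into the text. Silence on recency therefore cannot be taken as a waiver either.

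**3. Is there a check before enrolment?** Procedures places eligibility ahead of consent for every participant. The clinician call is described only for social-media and online-event responders, but that does not show that the other routes have no check. The patient-portal script and the event script are mentioned but not shown, so whether they carry a limit is unknown. What the check lacks is a date threshold.

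**4. What does the analysis depend on?** For each woman let d = score after − score before. The paired statistic is t = mean(d) / (s_d / √n), where s_d is the standard deviation of d and n is at most 50. Time since diagnosis does not enter it, so the test is equally valid for a cohort of new cases and for a mixed one.

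**5. What would a mixture do to the estimate?** Let p be the share of women with long-standing disease, and let δ_N and δ_L be the mean changes in new and long-standing cases. The expected mean change is (1 − p)·δ_N + p·δ_L. It differs from δ_N by p·(δ_L − δ_N). That difference is zero if p = 0 or if the two groups respond alike. The Protocol gives neither p nor δ_L − δ_N, so no size can be attached. Measured against the population in the Overall objectives, the mixture is simply part of the population under study.

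**The case for a change.** The best case for a change is that eligibility belongs in a protocol and cannot be left to an analysis plan. The word *newly* also cannot be dismissed as loose description, because the sentence that holds it is the only place where the disease itself is required. A check needs a rule, and here the rule has no threshold. The remedy would be cheap: define the term, or drop it.

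Much of this stands. The term is undefined, and the title, target population and advertisement are narrower than the objective. If the investigators are editing the document anyway, bringing these into line would do no harm.

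Two steps do not hold. The recruitment text, followed as written, only identifies and contacts women; it does not enrol anyone who fails the Target population paragraph. And no wrong result has been shown to follow. Harm needs both that long-standing cases are enrolled and that the result is claimed for new diagnoses alone. The Protocol fixes neither.

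The remedies also have a price. Recruitment of 50 women is planned over 4 to 6 weeks, that is 50/6 ≈ 8.3 to 50/4 = 12.5 per week. A narrow window could strain that pace, by an amount the Protocol does not let us derive. Rewording the advertisement, which has already been approved, would probably mean another review. That the Protocol does not mention recording time since diagnosis is no defect in itself, since such descriptive items usually belong on data collection forms or in an analysis plan, and neither is shown.

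**Conclusion.** No change to the plan is needed. This is missing operational detail that the study clinicians can settle at screening and the authors can settle by describing the cohort as enrolled. It is not a conflict between the eligibility and recruitment sections. The effect on the validity of the paired comparison is nil. The effect on interpretation is conditional and cannot be quantified from the Protocol. It disappears if the conclusion is worded as the Overall objectives section words it, for women with IC/BPS.

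This view rests on two assumptions. The first is that the eligibility requirement in Procedures is applied on every route, as its wording implies. The second is that the report does not claim the result specifically for new diagnoses without showing that the cohort consisted of them.

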[Previously IRB and Penn social media committee APPROVED]. We plan to have IC Association (non-profit organization supporting patients with IC) post the information about our study on their social media accounts (Facebook, Instagram, Twitter). The visual ad is attached (please note that Facebook and Instagram ads should contain less than 20% texts thus, we will relay the information required by the IRB and OCR in the text accompanying the visual ad. "If you have interstitial cystitis, Drs. [name] and [name] at the University of Pennsylvania's Division of Urogynecology are conducting a research study to teach patients how to self-manage their symptoms. In this completely remote, smartphone-based study, you will receive video treatment modules and check-in messages via a secure texting platform over 6 weeks (max 3 texts per week). If you are women over 18, recently diagnosed with IC, have a smartphone and interested in evidence-based, holistic ways to manage your symptoms, please call our study coordinator [name] at [contact]." Once they contact us through our study coordinator, we will set them up for a phone call with one of the clinicians on our team to confirm eligibility. They will then undergo remote consent and enrollment process with our study coordinator.

The following documents are currently attached to this item:

There are no documents attached for this item.

Subject compensation*

Will subjects be financially compensated for their participation?

No

The following documents are currently attached to this item:

There are no documents attached for this item.

If there is subject compensation, provide the schedule for compensation per study visit or session and total amount for entire participation, either as text or separate document

Study Procedures

Suicidal Ideation and Behavior

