Eligible participants will be consented via phone or video conferencing (patient choice) with our study coordinator. Then they will be asked to choose a treatment pathway that they are interested in (pelvic floor physical therapy, regulating brain-bladder connection, mindfulness practice). Then they will complete the following validated, published questionnaires: - Interstitial cystitis problem index - Interstitial cystitis symptom index - Pain self efficacy score - Hospital anxiety and depression score - Patient physician communication satisfaction. Then the patient will participate in a 6-week texting program. They will receive the following evidence-based, standard-of-care treatments for IC/BPS delivered via text messages: patient education about IC/BPS, urinary urge suppression exercise instructions, pelvic floor physical therapy instructions, mindfulness practices, cognitive behavioral therapy focusing on regulation the brain-bladder connection, and instruction on how to avoid common dietary triggers. Video modules will be texted out twice a week (Monday and Wednesday). Every Friday, they will receive a check-in message. If they report severe symptoms, they will be asked if they would like to be contacted via phone by a clinician to triage symptoms. After the completion of the program, the participants will complete the same set of questionnaires that they did at baseline. In addition, they will complete the Net Promoter Score and Systems Usability Scale, which are validated questionnaires to evaluate the quality of a technological program. Confidentiality will be maintained throughout the recruitment process as well as during study participation.

The following documents are currently attached to this item:

There are no documents attached for this item.

Deception

Does your project use deception? Deception could be considered any direct misinformation presented to the subject or omission of key information pertaining to the design or nature of the project.

No

International Research

Are you conducting research outside of the United States?

No

Analysis Plan

Response rate to text messages will be determined. We will also compare score of the validated questionnaires before and after participation in the texting project using paired t-test. P values 0.05 will be considered significant.

The following documents are currently attached to this item:

There are no documents attached for this item.

Subject Confidentiality

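### Does the unexplained choice among three treatment pathways leave the tested programme undefined?

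*Protocol*

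**What the plan says.** The Procedures section describes the sequence. The step after consent reads: "Then they will be asked to choose a treatment pathway that they are interested in (pelvic floor physical therapy, regulating brain-bladder connection, mindfulness practice". Participants then fill in the baseline questionnaires and enter the 6-week texting programme. Its content is introduced with "They will receive the following evidence-based, standard-of-care treatments for IC/BPS delivered via text messages". Six items follow, including "pelvic floor physical therapy instructions, mindfulness practices, cognitive behavioral therapy focusing on regulation the brain-bladder connection". The other three are education about the condition, urge suppression exercises and advice on dietary triggers.

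The same section gives the schedule: "Video modules will be texted out twice a week (Monday and Wednesday" for the modules, and "Every Friday, they will receive a check-in message". The recruitment text under Use of Penn Media & Social Media Services tells women that "you will receive video treatment modules and check-in messages via a secure texting platform over 6 weeks (max 3 texts per week".

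The selection of a pathway is mentioned nowhere else. The Protocol Description, Overall objectives, Analysis Plan and Consent Process all speak of one programme. The Design entry names a prospective cohort, without arms.

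**The concern.** Asking a woman to select one topic of three suggests that she will be given that topic and not the other two. Listing all three, without condition, among the treatments participants get suggests that everyone is given everything. The protocol does not say whether the selection governs content, order, emphasis or nothing.

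What would be at stake is the description of the intervention. If unchosen topics are left out, the list is not true of every woman, and the before-after result averages over up to three self-selected versions. If nothing is left out, an enrolment step has no stated purpose. Either way, someone wishing to repeat the programme could not tell from the protocol alone whether a given component went to all 50 women or only to those who picked it.

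**Working it through.** The protocol gives no figure on this point to reproduce. The check has three steps: compare the texts, test whether the schedule decides between the readings, and ask whether the analysis depends on the answer.

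**1. The texts side by side.** Three readings fit the Procedures section.

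| Reading | What the selection does | How the six-item list is then read | Women sent a given pathway topic |
|---|---|---|---|
| A | Nothing that affects content | Content for everyone | 50 |
| B | Decides which pathway topic is sent | Whole content of the programme, across pathways | 50/3 = 16.7, so 16 or 17 under an assumed even split; 0 to 50 possible |
| C | Sets order or emphasis | Content for everyone | 50 |

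Under B the list is loosely worded, but it still makes sense as the content of one programme: three common items plus three offered as options. The two sentences are therefore not shown to contradict each other. The text does not say which reading is meant.

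**2. The schedule.** Inputs are the two module days and one check-in day a week (Procedures), the 6 weeks, and the advertised cap of 3 texts a week.

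- Texts per week: 2 + 1 = 3, equal to the cap.
- Module sending occasions: 6 × 2 = 12.
- Check-ins: 6 × 1 = 6.
- Total: 12 + 6 = 18 texts.

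These counts fix the number of sending occasions. They do not fix the number of videos or topics per text, since the protocol speaks of modules in the plural and does not say how many go out each time. The cap therefore does not stop the selection from adding, removing or reordering content. The schedule fits A, B and C alike and cannot settle the question. Any estimate of the share of the programme given to unchosen topics would need assumptions about topics per video that the protocol does not supply.

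**3. The analysis.** For woman *i*, let *D_i* be the score after the programme minus the score before. The Analysis Plan uses

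t = mean(D) / (s_D / √n), with n − 1 degrees of freedom (50 − 1 = 49 if all 50 complete both assessments).

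Pathway does not enter this formula. Under A and C there is one content set, and mean(D) estimates the mean change after it. Under B, let w_k be the proportion choosing pathway *k*, with mean change μ_k and variance σ_k² among those who choose it. Then:

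- mean(D) estimates μ = Σ w_k μ_k, the mean change among women offered the programme with its built-in choice;
- s_D² estimates Σ w_k σ_k² + Σ w_k (μ_k − μ)², so differences between pathways are already in the standard error.

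Under every reading the test addresses the mean change in women given this programme, which is what Overall objectives sets out to study. The number enrolled, the 0.05 level and the response rate to texts do not depend on the reading either.

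**The case for a change.** The strongest case for a change is that a study of a single programme must say what the programme is, and that intervention content belongs in Procedures and cannot be left to the statistical analysis plan. That much is right. Treating the list as the whole library is something the reader has to supply. The protocol also does not say that the selected pathway is stored: Subject Confidentiality mentions demographic and questionnaire data. If content differs and the selection is not kept, it might be hard to establish later what each woman was sent.

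What stands is that one explanatory clause is missing. It weighs little, for three reasons. The Protocol Description says the programme had already been developed, so its message content exists apart from this paragraph and can be described from there. Subject Confidentiality also says that text messages are kept in a secure inbox, so, if outgoing messages are included, the content sent is likely to be recoverable. Finally, describing change by pathway would be an optional addition. No objective asks for it, and it would alter no planned result.

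**Conclusion.** The observation is accurate: a pathway is selected, all three topics are then listed without condition, and no section says what the selection does. It is a minor ambiguity in how the intervention is described and not a demonstrated contradiction. Its effect on the planned analysis is nil: the pooled before-after comparison suits the programme-level objective under each reading, and no number in the protocol moves. The uncertainty that remains is whether a given pathway topic reached all 50 women or a subset, about 16 or 17 under an assumed even split.

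This rests on the objective staying at programme level and on no claim being made for any single component or pathway. It concerns the pathway ambiguity only and says nothing about the other limits of an uncontrolled before-after design. The two sentences can be reconciled in a clause when the programme is described. Which delivery rule applies is for the investigator to state, and this review takes no position on it.
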